**8.6.1.5 Adverse events by dosage immediately before onset**

The number and incidence rate to total exposure period of adverse events and adverse drug reactions in overall and individual events classified by SOC and PT should be calculated by dose immediately before onset\*. The total exposure period is defined as the total number of days (days) that each dose was administered during the study period.

\*The tabulation unit by dose immediately before onset should be as follows:

MT-6548 group: daily dose (tabulation unit: 0 mg, 150 mg, 300 mg, 450 mg, 600 mg)

**8.6.1.6 Adverse events by cumulative dosage**

The number of subjects and incidence rate should be calculated for adverse events and adverse drug reactions by cumulative dosage before onset of AE for the overall events and for individual events classified by SOC and PT. The cumulative dosage will be divided into 4 categories at quartiles (0 to 1/4 of the maximum cumulative dosage, 1/4 to 2/4 of the maximum cumulative dosage, 2/4 to 3/4 of the maximum cumulative dosage,  $\geq 3/4$  of the maximum cumulative dosage). In addition, the average number of exposure days per subject should be tabulated for each category. (Average number of days of exposure: "0") – In the case of "0 to x/4 of the maximum cumulative dosage", the number of days until the subject reaches the x/4 of the maximum cumulative dosage should be calculated for each subject, and in the case of " $\geq 3/4$  of the maximum cumulative dosage", the number of days until the last dose should be calculated for each subject, and the mean value should be calculated).

**8.6.1.7 Adverse events before and after drug interruption**

The number of subjects and incidence rate should be calculated for adverse event and adverse drug reaction by before and after drug interruption for the overall and for individual events classified by SOC and PT. It should be classified to 2 categories: 4 weeks before drug interruption and 4 weeks after drug interruption (4 weeks after the start of drug interruption). If a subject had multiple drug interruptions and the adverse event occurred within 4 weeks after the drug interruption and within 4 weeks before the drug interruption, the subject should be counted as 1 subject for both periods.

Drug interruption period is defined as the "Planned start date of the modified dose" when "Yes" was selected in the query of "Did you choose the dosage according to the dosage adjustment algorithm?" and "Changed dose" = 0 mg in the query of "Whether the dose was changed" in the "Administration status of MT-6548" of the case report form. If "No" is selected for the query of "Did you choose dosage according to dosage adjustment algorithm?", the subject should not be included in the tabulation.

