#### (2) Treatment period

The treatment period will last from completion of scheduled tests on the first day of the treatment period to completion of blood sampling for haematology tests on the final day of the treatment period (Week 24 of the treatment period or discontinuation of treatment).

Treatment period study visits will be made every 2 weeks up until Week 12, and every 4 weeks thereafter for scheduled tests. However, study visits may be more frequent if variation in Hb levels causes concern for excessive increase or decrease in Hb, or for other reasons.

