#### Dosage adjustment algorithm for MT-6548 Tablet

- ✓ Dosage increases are in principle separated by at least 4 weeks. There are no set intervals for dosage decreases, but frequent dosage adjustments are to be avoided.
- ✓ Decrease MT-6548 dosage by 1 tablet if Hb levels suddenly increase (more than 2.0 g/dL change in past 4 weeks\*).
- ✓ Increase MT-6548 dosage by 1 tablet if Hb levels are <11.0 g/dL. However, decrease by 1 tablet instead of increasing in cases of sudden increase in Hb (more than 2.0 g/dL change in past 4 weeks\*).
- ✓ Decrease MT-6548 dosage by 1 tablet if Hb is >12.5 g/dL.
- ✓ If Hb is >13.0 g/dL and ≤13.5 g/dL, and there has been a sudden increase in Hb (more than 2.0 g/dL change in past 4 weeks\*), discontinue MT-6548 administration and resume at 1 tablet reduced dosage after Hb falls to ≤13.0 g/dL.
- ✓ If Hb is >13.5 g/dL, discontinue MT-6548 administration and resume at 1 tablet reduced dosage after Hb falls to ≤13.0 g/dL.

\*Calculate Hb change rate using the Hb measurement closest to 4 weeks prior to the day of dosage adjustment (in the range of 3 to 5 weeks). A rate of change greater than 0.5 g/dL/week constitutes “sudden increase.” If Hb was not measured 3 to 5 weeks prior to the day of dosage adjustment, use the measurement made immediately prior to 5 weeks before the day of dosage adjustment.

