#### 4.6 Number of days of drug interruptions

The number of days of drug interruptions does not include subject's missing to take the drug and is defined by the following formula. Number of days of drug interruptions (days) = Day of resumption of study drug administration – First day of study drug interruption

If there are multiple interruptions, the sum of them should be used.

Resumption day of study drug administration: After the entry of "Daily Dose" = 0 mg, the first dose should be taken when a value of >0 mg is entered for the first time. If the drug interruption continues until Week 24 of the treatment period, days should be calculated based on the visit date after Week 24 of the treatment period as the resumption date. However, if the treatment is completed or discontinued while the drug interrupted, the day of blood sampling for hematology tests at Week 24 or the day before the discontinuation of treatment should be used.

First day of study drug interruption: First day of administration when "Daily Dose = 0 mg is first entered in the CRF.

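### The adverse-event table around drug interruptions uses a fixed 28-day period after the start of a hold, not split at resumption and without person-days, so its before/after contrast can be diluted (minor)

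*SAP*

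**What the plan says.** SAP 8.6.1.7 asks for the number of subjects and the incidence rate of AEs and adverse drug reactions, overall and by SOC and PT, before and after a hold. The two periods are "4 weeks before drug interruption and 4 weeks after drug interruption (4 weeks after the start of drug interruption"; SAP 8.6.11 equates 4 weeks with 28 days. The hold is dated by the "Planned start date of the modified dose" entered in the CRF when the dose becomes 0 mg. No end date enters the definition. Only holds chosen under the dosage adjustment algorithm qualify; where the CRF answer to that question is No, "the subject should not be included in the tabulation".

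Repeated holds have their own rule: "If a subject had multiple drug interruptions and the adverse event occurred within 4 weeks after the drug interruption and within 4 weeks before" a hold, then "the subject should be counted as 1 subject for both periods".

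Four other places bear on this:

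- SAP 4.6 defines when a hold ends: "Number of days of drug interruptions (days) = Day of resumption of study drug administration – First day of study drug interruption".
- The algorithm in Protocol 8.3 says to "discontinue MT-6548 administration and resume at 1 tablet reduced dosage after Hb falls to" 13.0 g/dL or below. It states no minimum length of hold, and Protocol 8.3 also allows dose changes at unscheduled visits.
- Protocol 5.2 sets the visit spacing: "Treatment period study visits will be made every 2 weeks up until Week 12", and every 4 weeks after that.
- The SAP errata do not alter 8.6.1.7. Their change to 4.6 concerns only holds still open when treatment ends.

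**The concern.** A table headed before and after interruption invites the reader to compare drug taken with drug stopped. Three features make the columns poor stand-ins for that comparison.

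1. The *after* period continues past resumption, so it can mix days off drug with days on resumed drug.
2. With repeated holds, the *after* period of one hold can overlap the *before* period of the next.
3. AEs are counted only from study drug administration (Protocol 9.2.4.2, SAP 8.6.1.1), so an early hold has fewer *before* days than *after* days. The section asks for an incidence rate but does not say what it is divided by.

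If AEs are more frequent on drug, a real fall after stopping could look in this table like little or no change.

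**Working it through.** The plan states no figure for this table, so there is nothing to reproduce. The check is day-counting, followed by one conditional calculation of dilution. That the *after* period runs past resumption is inferred: 8.6.1.7 has no rule ending it there and uses a start date only. Nothing in the documents contradicts this.

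**Inputs from the documents.** Both periods are 28 days, anchored on hold start. Nominal visit days (Protocol Table 9.1-1) are 14, 28, 42, 56, 70, 84, 112, 140 and 168. Hold lengths and gaps between holds are not given, so they are varied below.

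**Step 1: resumed-drug days in the *after* period** = max(0, 28 − hold length).

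| Hold length (days) | Days on resumed drug | Share of 28 |
|---|---|---|
| 7 | 21 | 75% |
| 14 | 14 | 50% |
| 21 | 7 | 25% |
| 28 or more | 0 | 0% |

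On nominal days, a hold started at Weeks 2 to 10 can end at the next visit 14 days later, leaving 14 of 28 days on drug. From Week 12 the next visit is 28 days on, which leaves none. Permitted visit ranges (±3 days to Week 12, ±7 days later) shift these counts somewhat, and an unscheduled visit can end a hold at any time.

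**Step 2: overlap for two holds in one subject.** With hold starts *g* days apart, *after* of hold 1 covers days 0 to 28 and *before* of hold 2 covers days *g* − 28 to *g*. For *g* of 28 or more, the overlap is max(0, 56 − *g*).

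| Gap between starts (days) | Shared days |
|---|---|
| 28 | 28 |
| 35 | 21 |
| 42 | 14 |
| 49 | 7 |
| 56 or more | 0 |

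At 28 days (stop Week 6, resume Week 8, stop Week 10) the two periods are the same days. If the first hold lasted 14 days, 14 of the second hold's 28 *before* days were off drug. With one hold there is no overlap.

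**Step 3: early holds.** On nominal days only a Week 2 hold (Day 14) is affected: 14 *before* days against 28 *after* days. Week 4 is Day 28 and has a full *before* period.

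**Step 4: dilution, if risk is higher on drug.** Let daily hazards be constant, λ₁ on drug (the same after resumption as before the hold) and λ₀ off drug, with a hold of *d* days (28 at most).

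- *Before* cumulative hazard = 28λ₁.
- *After* cumulative hazard = dλ₀ + (28 − d)λ₁.
- Difference = d(λ₁ − λ₀), against 28(λ₁ − λ₀) for a hold of 28 days.

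The fraction of the contrast kept is d/28 whatever the two rates: 25% at 7 days, 50% at 14, 75% at 21.

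To show this as incidence, assume 28-day incidences of 40% on drug and 20% off drug. Neither figure is in the documents. Then *after* incidence = 1 − 0.8^(d/28) × 0.6^(1 − d/28).

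| Hold (days) | *Before* | *After* | Difference (points) |
|---|---|---|---|
| 28 | 40% | 20.0% | 20.0 |
| 21 | 40% | 25.6% | 14.4 |
| 14 | 40% | 30.7% | 9.3 |

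For a Week 2 hold, the 14-day *before* incidence on the same assumption is 1 − 0.6^0.5 = 22.5%, against 40% for a full period at an unchanged rate.

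**The case against.** **The purpose is inferred.** A reader might conclude that 8.6.1.7 sets out to compare AEs on and off drug and fails. The section does not say so. It states openly that *after* is counted from the start of the hold and never calls that period off-drug. Because only algorithm holds qualify, and these are triggered by high Hb, the table can fairly be read as describing AEs around such a hold. A fixed window is a legitimate choice for that, and SAP 8.6.11 uses a similar 28-day reference for Hb. This stands: what is missing is a label and a split.

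**Exposure is handled elsewhere.** SAP 8.6.1.5 tabulates AEs by dose just before onset, including 0 mg, against total days at each dose. A reader might infer that the trial could miss a fall in AEs on stopping; that table means the documents do not support going so far. It mitigates only in part, since it pools over subjects and time and does not show what happens around a hold.

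**Counting in both periods is deliberate.** It is a stated rule about subjects, not a slip. It needs two qualifying holds with starts under 56 days apart. Full coincidence at 28 days would need Hb to fall to the resumption level and then meet a hold threshold again within 2 weeks on one tablet less. The documents do not say how often any of this happens.

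**Early holds should be few.** Entry requires mean screening Hb below 11.0 or 12.5 g/dL by cohort, and patients thought likely to need an immediate drug holiday are excluded.

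**The numbers are small and assumed.** The 40% and 20% are illustrative. Resumption is at a reduced dose, so the resumed-drug hazard may be lower than assumed, and carry-over is ignored. If 10 of the 40 subjects were held (an assumption), going from 20.0 to 9.3 points is 0.107 × 10, or about one subject. The section specifies no test or confidence interval.

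**Ending the window at resumption would bring its own bias.** Its length would then depend on how fast Hb falls, and later-onset AEs would be lost. This also stands, and it is why the fixed window should stay.

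**Conclusion.** The point holds in limited form. The *after* column can contain resumed-drug days whenever a hold is shorter than 28 days. One AE can put a subject in both columns when qualifying holds start less than 56 days apart. On nominal visit days, a Week 2 hold has half the *before* time, with no person-days to show it.

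If risk is higher on drug, the mixing and the overlap move the contrast toward zero, and the short *before* period lowers the *before* count. Under constant hazards, with the pre-hold rate returning on resumption, a 14-day hold keeps half the contrast. If risk does not differ on and off drug, resumed days cause no dilution. The size in this trial cannot be stated without hold lengths and frequencies.

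The effect is confined to one descriptive safety table and does not touch the primary endpoint, so it is minor. The documents do not support a claim that the safety analysis as a whole is biased, or that the rule for repeated holds is an error.

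**What to change.** In SAP 8.6.1.7, keep the fixed 28-day window and:

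- label the second column *within 28 days of hold start*;
- split its AEs at the SAP 4.6 resumption day into still interrupted and resumed;
- show person-days observed for each column, with *before* starting no earlier than first dose;
- report how many subjects appear in both columns.

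This needs only dose and date entries already in the CRF, and it follows the exposure reporting in SAP 8.6.1.5 and 8.6.1.6. The cost is some wording, modest programming, and a slightly larger table with small cells. If the data are already locked, Protocol 13.4 requires the reason to be given and the result to be distinguished from the original plan. No dosing or hold rule changes.

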#### MT-6548 Tablet dosage adjustment guidelines

Investigators/subinvestigators will monitor Hb levels throughout the treatment period, and determine whether to adjust study drug dosage or discontinue administration as required. In principle dosage adjustments are to be performed at scheduled study visits, but they may also be performed at unscheduled visits if considered necessary, for example if Hb level variation gives concern for excessive increases or decreases.

Hb levels will be measured on scheduled study visit with the HemoCue® Hb201 DM analyzer; in principle these measurements will be used for determinations regarding dosage adjustments. Hb measurements used for dosage adjustment determinations will be recorded in the subject's case report form (CRF). Measurement results from the HemoCue® Hb201 DM will be used solely for determination of study drug dosage adjustments, and will not be used for efficacy or safety analysis.

The dosage adjustment algorithm below will be followed in order to maintain Hb levels of 11.0–13.0 g/dL during the study. Dosage adjustment steps are defined in the chart below.

MT-6548 Tablet dosage adjustment chart

Step	No. of tablets	Dosage
1	1	150 mg
2	2	300 mg
3	3	450 mg
4	4	600 mg

\*It is permitted for dosage adjustments not to comply with the dosage adjustment algorithm for safety reasons depending on factors such as clinical status (e.g., AEs, volume depletion, or volume overload), Hb elevation rate, decrease rate, or fluctuations. In such cases, clinical status will be recorded in CRFs. All dosage increases of MT-6548 will be in increments of 1 tablet at a time.

If a dosage increase or reduction according to the dosage adjustment algorithm is impossible because the maximum or minimum dosage on the dosage adjustment chart is already being administered, it is permitted to not alter the dosage at that point. However, in this case it will be confirmed whether withdrawal criteria are met, and treatment discontinued if so.

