##### (1) ESA formulations

If a subject has received maximum dosages of MT-6548 for  $\geq 2$  weeks and meets all criteria below, investigators/subinvestigators may administer ESA as rescue therapy to improve Hb levels if necessary in order to secure subject safety. ESA rescue therapy may also be administered without meeting the criteria below if deemed necessary by investigators/subinvestigators in order to secure subject safety, such as in cases of acute decreases in Hb. MT-6548 administration will be discontinued if implementing ESA rescue therapy. Study drug treatment may resume if Hb levels improve, as long as there is no concomitant use with ESA. Subjects who are not expected to resume study drug treatment will

be withdrawn from the study.

- ✓ Anaemia or anaemia symptoms (e.g., fatigue, weakness, shortness of breath, chest pain, confusion, dizziness) become aggravated compared to the first day of the treatment period to the point they are clinically problematic.
- ✓ Hb levels drop to <8.0 g/dL.

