### 8.2.2 Subjects who discontinued or interrupted their treatment

For subjects enrolled in the treatment period, the number and proportion of subjects who discontinued treatment should be tabulated based on each reason.

Item: Number and proportion of discontinued subjects who enrolled in the treatment period and the number and proportion of reasons for discontinuation.

For subjects enrolled in the treatment period, the number of drug interruptions and the number and proportion of drug interruptions by reasons for drug interruption should be tabulated. The denominator of the proportion should be the sum of the number of interruptions. If there are multiple reasons for a single interruption, they should be counted for each reason and stated as the number of interruption cases.

Item: Number of cases of interruptions of the study drug in subjects who enrolled in the treatment period and the number and proportion of drug interruptions by reasons for study drug interruptions

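### The table of adverse events before and after drug interruption covers only holds marked as following the Hb algorithm, and it drops the subject, not just the hold, when the answer is No

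*SAP*

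**What the plan says.** SAP 8.6.1.7 uses two CRF answers to identify an interruption: the dose was chosen by the algorithm (Yes), and the changed dose is 0 mg. The planned start date of that change anchors the two 4-week windows. For a No on the algorithm question, the section ends by saying that "the subject should not be included in the tabulation". It gives no reason for the restriction, and the errata to SAP Version 2 do not touch it.

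Protocol 8.3 contains two steps that stop drug. One applies above 13.5 g/dL, and the other applies above 13.0 and up to 13.5 g/dL with a sudden rise. In both the instruction is to "discontinue MT-6548 administration and resume at 1 tablet reduced dosage after Hb falls to" 13.0 g/dL or below. The same section provides for departures: "It is permitted for dosage adjustments not to comply with the dosage adjustment algorithm for safety reasons depending on factors such as clinical status", and adverse events are the first example given.

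Protocol 8.5.3 adds a stop that is not part of the algorithm: "MT-6548 administration will be discontinued if implementing ESA rescue therapy". That stop can be temporary: "Study drug treatment may resume if Hb levels improve, as long as there is no concomitant use with ESA".

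Elsewhere the SAP treats interruptions without this filter. Section 4.6 starts an interruption when a daily dose of "0 mg is first entered in the CRF", whatever the reason. Section 8.2.2 says that "the number of drug interruptions and the number and proportion of drug interruptions by reasons for drug interruption should be tabulated".

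**The concern.** The heading of 8.6.1.7 promises adverse events before and after drug interruption, with no qualifier. A reader of the output would take it to cover interruptions as defined in SAP 4.6 and counted in 8.2.2. It covers a subset, and the filter is related to why drug was stopped: holds triggered by Hb under the algorithm stay in, and holds prompted by an adverse event or by rescue probably do not.

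The exclusion is also worded at the level of the subject, although the definition just before it works entry by entry. Programmers could implement it differently and obtain different counts and denominators.

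What is at stake is the interpretation of one descriptive safety table. It is the only planned output that lines up adverse events with fixed windows either side of a hold.

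**Working it through.** The plan states no figure on this point and there is nothing to recompute. The check is a comparison of the sections.

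**Step 1: which holds can be marked Yes.** The algorithm in Protocol 8.3 stops drug only on the two high-Hb triggers. Every other step is an increase or a decrease of one tablet. Below 11.0 g/dL it calls for an increase, or for a decrease after a sudden rise, but never for a stop.

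**Step 2: how other holds would be marked.** The expected answers below are inferred from Protocol 8.3 and 8.5.3.

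| Type of hold | Where it comes from | Expected answer | In the 8.6.1.7 table? |
|---|---|---|---|
| Hb above 13.5 g/dL, or above 13.0 to 13.5 g/dL with a sudden rise | Protocol 8.3, algorithm | Yes | Yes |
| Hold for an adverse event, no Hb trigger met | Protocol 8.3, permitted departure | No | No |
| Temporary stop for ESA rescue | Protocol 8.5.3 (1) | No | No |
| Hold for an adverse event when an Hb trigger is also met | Both | Could be Yes | Possibly |

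The protocol expects the second kind. Drug holiday is one of the coded actions taken for an adverse event in Protocol 9.2.4.2. Some ESA-rescue stops are not interruptions at all, because subjects not expected to resume are withdrawn.

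**Step 3: what the exclusion sentence removes.** It names neither the interruption nor the 0 mg condition. Three readings are possible:

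- (a) Any No at any dose decision, including one that was not a hold, removes the subject. This is the literal reading.
- (b) Any No at a change to 0 mg removes the subject.
- (c) A No at a change to 0 mg removes only that interruption.

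A subject with one algorithm hold and one hold for an adverse event is lost under (a) and (b), but is kept for the algorithm hold under (c). A subject with one algorithm hold and a No at a dose change that was not a hold is lost only under (a).

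**Step 4: what the other outputs cover.**

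| Output | Algorithm filter | What it lacks for this question |
|---|---|---|
| SAP 8.2.2, interruptions by reason | None | No adverse events |
| SAP 8.6.1.1 and 8.6.1.2, adverse events leading to dose reduction or interruption | None | Shows the event that led to the hold, not what followed |
| SAP 8.6.1.5, adverse events by dose just before onset, with a 0 mg row | None | Not aligned to the hold date; no matching window before; not split by reason; later events move to another row once drug resumes |
| SAP 8.6.11, Hb at and about 4 weeks after reduction or interruption | None | Hb only |

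The errata keep the 8.6.1.2 tabulation of adverse events leading to dose reduction or interruption. Together these outputs cover much of the ground, but none shows adverse events in the 4 weeks before and after a non-algorithm hold.

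**Step 5: size.** The documents give neither the number of holds nor their split by reason. Any proportion of subjects excluded would be invented.

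**The case against.** The strongest defence is that the restriction makes a cleaner comparison. When an adverse event causes the hold, that event tends to sit in the before window by construction. After ESA rescue, the after window reflects ESA as well as the absence of study drug. Pooling all holds would therefore bias the comparison, and a table limited to Hb-triggered holds answers a narrower question better. This stands as an argument against pooling. It does not explain why the other holds appear nowhere in this form, why a whole subject is dropped, or why the SAP gives no rationale.

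It can also be said that 8.6.1.7 states its own definition openly, whereas SAP 4.6 exists to derive days of interruption for exposure and compliance. That is fair: the two differ without contradicting each other. The heading still gives no sign of the narrower scope.

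A reader might infer more than the documents support:

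- **That the plan removes the holds that matter for safety.** Excessive or rapid Hb rise is itself a safety concern in Protocol 5.3.2, and the algorithm holds respond to it.
- **That adverse events after other holds are not tabulated.** Events arising at 0 mg appear in SAP 8.6.1.5 whatever the reason for the hold.
- **That no adverse-event or rescue hold can enter the table.** This needs every such hold to be marked No, and the CRF completion rule is not available.
- **That a subject with mixed holds is certainly lost.** This is the literal reading of a translated sentence, and reading (c) is possible.

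**Conclusion.** The point holds in limited form. SAP 8.6.1.7 restricts its table to holds marked as following the algorithm and, as worded, excludes the subject rather than the interruption. Holds for adverse events or ESA rescue are very likely absent, and a subject with a valid algorithm hold may be lost as well. The first conclusion assumes that sites mark such holds No, as Protocol 8.3 and 8.5.3 imply. The second assumes the literal reading of the last sentence.

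The consequence is confined to one supplementary descriptive table in a single-arm study, with no decision rule attached. The number of subjects affected cannot be estimated. Severity is minor; the change is a cheap improvement.

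**What to change.** 1. Replace the last sentence of SAP 8.6.1.7 so that a change to 0 mg marked No is left out of this table while the subject's algorithm holds still count. State that a No at a dose decision that was not a hold has no effect.
2. Title the existing table as algorithm (Hb-triggered) holds and give the reason for the restriction in one line.
3. Add a separate block, or a listing if few subjects are involved, for all other 0 mg holds. Split it by the reason recorded in the CRF under Protocol 9.2.2: adverse event, ESA rescue, other. A subject with both kinds of hold appears in both places. Do not pool the blocks.
4. Footnote that the before window of a hold made for an adverse event contains the triggering event by construction, and that ESA affects the after window of a rescue hold.

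The cost is a wording change and one extra block or listing from data already collected. The downside is that the before column for holds made for adverse events will be inflated, so it must not be read as an effect of stopping drug. If the data are already locked, Protocol 13.4 allows the addition, provided that the reason is given and the result is kept distinct from the original plan.
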